9.7 Safety Analysis

Safety data will be summarized by treatment group with descriptive statistics and frequency tables. In general, continuous data will be summarized by presenting the number of subjects, mean, standard deviation, median, minimum, and maximum values. Categorical data will be summarized by presenting the number (frequency) and percentage of subjects at each level of response. Subject disposition will be presented and summarized.

Adverse events will be coded using MedDRA, Version 23.0 or higher, by system organ class and preferred term, and a listing of all AEs will be generated. Treatment-emergent AEs (TEAEs), treatment-related TEAEs, TEAEs by intensity, TEAEs that lead to discontinuation of study drug, and SAEs will be summarized by treatment, system organ class, and preferred term.

The clinical laboratory data will be summarized by time point, treatment group, and change from baseline. The values that are below the lower limit or above the upper limit of the reference range will be flagged. Those values or changes in values that are considered clinically significant by the investigator will also be flagged. Repeated or unscheduled results will not be included in the summary statistics but will be included in the individual data listings.

9.8 Interim Analyses

None planned.

10. DATA HANDLING AND QUALITY ASSURANCE

10.1 Data Security

The study data will be collected electronically. This electronic data capture (EDC) system complies with ICH GCP, GDPR, and the current 21 CFR Part 11 guidance, Electronic Records and Signatures.

10.2 Case Report Forms

As part of the responsibilities assumed by participating in the study, the principal investigator agrees to maintain adequate case histories for the subjects treated as part of the research under this protocol. The principal investigator agrees to maintain accurate eCRFs and source documentation as part of the case histories.

OncoNano Medicine will supply the eCRF. All eCRF information is to be filled in. If an item is not available or is not applicable, this fact will be indicated. The eCRF has an electronic audit trail so changes can be made until the investigator signs the eCRF. Each completed eCRF must be reviewed, signed, and dated by the principal investigator in a timely manner. The completed eCRF will be collected by study monitors as soon as practical after completion. One copy will remain at the site in the principal investigator's files.

10.3 Monitoring of the Study

The clinical monitor, as a representative of OncoNano Medicine, has the obligation to follow the study closely. In doing so, the monitor will visit the principal investigator and study facility at periodic intervals, in addition to maintaining necessary contact through telephone, email, and letter. The monitor will maintain current personal knowledge of the study through observation, review of study records and source documentation, and discussion of the conduct of the study with the principal investigator and staff.

All aspects of the study will be carefully monitored, by OncoNano Medicine or its designee, for compliance with applicable government regulation with respect to current International Conference on Harmonisation (ICH) harmonised tripartite guideline E6(R1): Good Clinical Practice and current standard operating procedures.

10.4 Inspection of Records

The principal investigator and institutions involved in the study will permit trial-related monitoring, audits, institutional review board (IRB) review, and regulatory inspection(s) by providing direct access to all study records. In the event of an audit, the principal investigator agrees to allow OncoNano Medicine, representatives of OncoNano Medicine, the United States Food and Drug Administration (FDA), and/or other regulatory agency access to all study records.

The principal investigator should promptly notify OncoNano Medicine of any audits scheduled by any regulatory authorities and promptly forward copies of any audit reports received to OncoNano Medicine.

10.5 Study Record Retention

Essential documents should be retained until at least 2 years after the last approval of a marketing application in an ICH region and until there are no pending or contemplated marketing applications in an ICH region or at least 2 years have elapsed since the formal discontinuation of clinical development of the investigational product. These documents should be retained for a longer period, however, if required by the applicable regulatory requirements or by an agreement with OncoNano Medicine. It is the responsibility of OncoNano Medicine to inform the principal investigator as to when these documents no longer need to be retained.

11. ADMINISTRATIVE CONSIDERATIONS

The following administrative items are meant to guide the principal investigator in the conduct of the trial but may be subject to change based on industry and government standard operating procedures or working practice documents or guidelines. Administrative changes will be reported to the IRB but will not result in protocol amendments.

11.1 Confidentiality

All laboratory specimens, evaluation forms, reports, and other records will be identified in a manner designed to maintain subject confidentiality. All records will be kept in a secure storage area with limited access. Clinical information will not be released without the written permission of the subject (or the subject's guardian), except as necessary for monitoring and auditing by OncoNano Medicine, its designee, the FDA, or the IRB.

The principal investigator and all employees and coworkers involved with this study may not disclose or use for any purpose other than performance of the study, any data, record, or other unpublished, confidential information disclosed to those individuals for the purpose of the study. Prior written agreement from OncoNano Medicine or its designee must be obtained for the disclosure of any said confidential information to other parties.

11.2 Institutional Review Board/Ethics Committee Approval

Federal regulations and the ICH guidelines require that approval be obtained from an IRB before participation of human subjects in research studies. Before the study onset, the protocol, informed consent, advertisements to be used for subject recruitment, and any other written information regarding this study to be provided to the subject or the subject's legal guardian must be approved by the IRB. Documentation of all IRB approvals and of the IRB compliance with ICH E6(R1) will be maintained by the site and will be available for review by OncoNano Medicine or its designee.

All IRB approvals should be signed by the IRB chairman or designee and must identify the IRB name and address, the clinical protocol by title and/or protocol number and the date approval and/or favorable opinion was granted.

The principal investigator is responsible for obtaining continued review of the clinical research at intervals not exceeding 1 year or otherwise specified by the IRB. The principal investigator must supply OncoNano Medicine or its designee with written documentation of continued review of the clinical research.

11.3 Modification of the Protocol

Any changes in this research activity, except those necessary to remove an apparent, immediate hazard to the subject, must be reviewed and approved by OncoNano Medicine or its designee. Amendments to the protocol must be submitted in writing to the principal investigator's IRB for approval before subjects are enrolled into an amended protocol.

11.4 Informed Consent

A written informed consent in compliance with Part 50 of Title 21 of the Code of Federal Regulations (CFR) shall be obtained from each subject before entering the study or performing any unusual or nonroutine procedure that involves risk to the subject. An informed consent template may be provided by OncoNano Medicine to investigative sites. If any institution-specific modifications to study-related procedures are proposed or made by the site, the consent should be reviewed by OncoNano Medicine and/or its designee, if appropriate, before IRB submission. Once reviewed, the consent will be submitted by the principal investigator to their IRB for review and approval before the start of the study. If the informed consent form is revised during the course of the study, all active participating subjects must sign the IRB-approved revised form.

Before recruitment and enrollment, each prospective subject will be given a full explanation of the study and allowed to read the approved informed consent form. Once the principal investigator is assured that the subject understands the implications of participating in the study, the subject will be asked to give consent to participate in the study by signing the informed consent form.

The principal investigator shall provide a copy of the original form of the signed informed consent to the subject and/or legal guardian.

11.5 Protocol Violations and Deviations

The principal investigator or designee must document and explain in the subject's source documentation any deviation from the approved protocol. The principal investigator may implement a deviation from or a change of the protocol to eliminate an immediate hazard to trial subjects without prior IRB approval. As soon as possible after such an occurrence, the implemented deviation or change, the reasons for it, and any proposed protocol amendment(s) should be submitted to the IRB for review and approval, to OncoNano Medicine for agreement, and to the regulatory authorities, if required.

A deviation from the protocol is an unintended and/or unanticipated departure from the procedures and/or processes approved by OncoNano Medicine and the IRB and agreed to by the

principal investigator. Deviations usually have an impact on individual subjects or a small group of subjects and do not involve inclusion/exclusion or primary endpoint criteria. A protocol violation occurs when there is nonadherence to the protocol that results in a significant, additional risk to the subject, when the subject or principal investigator has failed to adhere to significant protocol requirements (inclusion/exclusion criteria) and the subject is enrolled without prior approval by OncoNano Medicine, or when there is nonadherence to FDA regulations and/or ICH E6(R1) guidelines.

The clinical monitor will document protocol violations and deviations throughout the course of monitoring visits. The monitor will notify the principal investigator during a visit and/or in writing of all violations and deviations. The IRB should be notified of all protocol violations and deviations in a timely manner.

11.6 Study Reporting Requirements

By participating in this study, the principal investigator agrees to submit reports of SAEs according to the timeline and method outlined in the protocol. In addition, the principal investigator agrees to submit annual reports to their IRB as appropriate. The principal investigator also agrees to provide OncoNano Medicine with an adequate report shortly after completion of the principal investigator's participation in the study.

11.7 Investigator Documentation

Before beginning the study, the principal investigator will be asked to comply with ICH E6(R1) 8.2 and 21 CFR by providing the following essential documents, including but not limited to:

- An original investigator-signed Investigator Agreement page of the protocol
- An IRB-approved informed consent, samples of site advertisements for recruitment for this study, and any other written information regarding this study that is to be provided to the subject or legal guardians
- IRB approval
- Form FDA 1572, fully executed, and all updates on a new fully executed Form FDA 1572
- Curriculum vitae (CV) for the principal investigator and subinvestigators listed on Form FDA 1572. Current licensure must be noted on the CV. They will be signed and dated by the principal investigator at study start-up, indicating that they are accurate and current
- Financial disclosure information to allow OncoNano Medicine to submit complete and accurate certification or disclosure statements required under 21 CFR 54. In addition, the investigators must provide to OncoNano Medicine a commitment to promptly update this information if any relevant changes occur

during the course of the investigation and for 1 year following the completion of the study

- Laboratory certifications and reference ranges for any local laboratories used by the site, in accordance with 42 CFR 493

11.8 Study Conduct

The principal investigator agrees that the study will be conducted according to the principles of the ICH E6(R1) guidelines and the principles of the World Medical Association Declaration of Helsinki. The principal investigator will conduct all aspects of this study in accordance with all national, state, and local laws or regulations.

11.9 Publications

Following completion of the study, the data may be considered for reporting at a scientific meeting or for publication in a scientific journal. In these cases, OncoNano Medicine will be responsible for these activities and will work with the investigators to determine how the manuscript is written and edited, the number and order of authors, the publication to which it will be submitted, and other related issues. OncoNano Medicine has final approval authority over all such issues.

Data are the property of OncoNano Medicine and cannot be published without prior authorization, but data and publication thereof will not be unduly withheld.

13. APPENDIX 1: SCHEDULE OF EVENTS (GROUPS 1 AND 2)

[figure not shown]
Evaluation	Screening	Treatment			
	Days -30 to 0	Day 0	Sur er postdose)	Day 10 (±5 days) or Day of Discharge	Day 28 (± 5 days)
Informed consent & subject enrollment	X				
Inclusion/exclusion criteria	X	X			
Blood/Urine/Breath alcohol		X			
Pregnancy test ^a	X	X			X
Demographic data	X				
Medical history	X				
Physical examination	X			X	
Karnofsky Performance Status	X				
Height ^b	X	X			
Body weight ^b	X	X			
Vital signs ^c	X	X	X ^d	X	X
12-lead electrocardiogram		X ^e		X	
Concomitant medications	X	X	X	X	X
Study drug administration		X ^f			
Adverse events review ^g		X	X	X	X
Serum chemistry	X	X	X	X	X
Hematology ^h	X	X	X	X	X
Surgery			X		
Intraoperative Imaging			X		
Pathology evaluation of surgical specimens			X ⁱ		

Footnotes

[figure not shown]
- ^a For female subjects, a serum sample for a serum pregnancy test will be collected at screening and on Day 0 and Day 28.
- ^b Body mass index will be calculated at Screening only.
- ^c Vital sign measurements will include systolic and diastolic blood pressure, pulse, respiratory rate, and temperature (in degrees Celsius). Blood pressure and pulse will be measured after a resting period of at least 5 minutes in the supine position.
- ^d Vitals are only to be collected if they are found to be abnormal at dosing
- ^e 12-lead ECG is to be performed prior to study drug administration
- ^f Prophylactic diphenhydramine may be administered prior to the administration of pegsitacianine
- ^g Patients will be assessed for AEs occurring from the time of dosing through Day 28 (± 5 days)
- ^h Hematology assessments will include hemoglobin, hematocrit, erythrocyte count (red blood cells), differential leukocytes, platelet count, and total leukocytes (white blood cells).
- ⁱ Pathologic analysis of surgical specimens will take place from the conclusion of surgery and up to 10 days after

14. APPENDIX 2: COMPLETENESS OF CYTOREDUCTION SCORE

**COMPLETENESS OF CYTOREDUCTION
AFTER SURGERY (CC SCORE)**

15. APPENDIX 3: PERITONEAL CARCINOMATOSIS INDEX

Regions	Lesion Size
0 Central	_____
1 Right Upper	_____
2 Epigastrium	_____
3 Left Upper	_____
4 Left Flank	_____
5 Left Lower	_____
6 Pelvis	_____
7 Right Lower	_____
8 Right Flank	_____
9 Upper Jejunum	_____
10 Lower Jejunum	_____
11 Upper Ileum	_____
12 Lower Ileum	_____

PCI

Lesion Size Score
LS 0 No tumor seen
LS 1 Tumor up to 0.5 cm
LS 2 Tumor up to 5.0 cm
LS 3 Tumor > 5.0 cm or confluence

ROC	receiver operating characteristic
SAE	Serious adverse event
SBR	specimen to background ratio
SOC	Standard of care
SUSAR	suspected unexpected serious adverse reaction
SWI	sterile water for injection
TBR	tumor to background ratio

1. INTRODUCTION

This Statistical Analysis Plan covers the statistical analysis and reporting for the protocol ON-1003 dated 23JUN2021. A detailed list of tables, listings and figures (TLFs) will be supplied in a separate, version-controlled document.

In case of discrepancies between the SAP and the protocol, the SAP will overwrite the protocol with respect to analyses and reporting.

2. STUDY OBJECTIVES

2.1 Objectives and Endpoints

The main objective of this study is to investigate whether pegsitarcianine can detect residual disease in the peritoneal cavity following standard of care (SOC) resection of peritoneal metastases using a [REDACTED] mg/kg dose administered [REDACTED] prior to surgery.

Table 1. Objectives and Endpoints

Objectives	Endpoints
Primary Objective	Primary Endpoint

The primary objective of this study is to determine if administration of pegasitacianine (█ mg/kg) results in the detection of metastatic disease left behind following standard of care surgical resection of peritoneal metastases.
	
Rate of detection of disease left behind following SOC resection of peritoneal metastases as measured by rate of Clinically Significant Events (CSEs).

Secondary Objectives	Secondary Endpoints

Demonstrate reliable sensitivity, specificity, negative predictive values (NPPV), and positive predictive values (PPV) of the imaging agent at the level of the individual specimens.
	
Sensitivity, specificity, negative predictive values (NPV), and positive predictive values (PPV).

Demonstrate an acceptable safety profile.	Incidence of TEAEs and SAEs, abnormalities in lab values, vital signs, or ECG results.
Exploratory Objectives	Exploratory Endpoints
Assess the how the normalized SBR value affects the diagnostic accuracy of pegsitacianine in detection of metastatic disease vs. normal tissue.	ROC analysis across various specimen-to-background ratio fluorescence thresholds.
Effect of camera system on diagnostic results.	Diagnostic results across various camera systems.
Assess amount of fluorescence shown in various types of specimens.	Mean fluorescence intensity and Specimen-to-background ratio

3. STUDY DESCRIPTION

3.1 Study Design

This Phase 2 study will be an interventional, open-label, single arm trial where each patient is his/her own “intrapatient” control using two Groups. All patients will receive a single █ mg/kg dose of pegsitacianine administered █ prior to standard of care surgery.

Patients enrolled in Group 1 of the study will have a biopsy confirmed diagnosis of non-mucinous peritoneal carcinomatosis, defined as less than 50% mucin in the sample, with a suspected Peritoneal Carcinomatosis Index (PCI) greater than or equal to 10. Group 2 of the study will include patients with a suspected PCI greater than or equal to 10 and a biopsy confirmed diagnosis of mucinous peritoneal carcinomatosis, defined as > 50% mucin in the sample. A total of approximately 60 patients will be enrolled across both Groups. Enrollment will be open first to Group 1 with the opportunity to open Group 2 for enrollment at the discretion of the sponsor.

In both Groups 1 and 2, the surgeon will perform their SOC resection of visible metastases and image each resected specimen, and normal specimens on an area of normal tissue outside of the surgical field using the intraoperative NIR camera; no NIR imaging of the peritoneal cavity will be performed at this time. At the conclusion of SOC resection, the intraoperative NIR camera will be used to investigate the peritoneal cavity further for evidence of residual metastases highlighted by fluorescence using an approach similar to that performed for the calculation of the Peritoneal Carcinomatosis Index (i.e., 13 regions). Additional fluorescent specimens will also be imaged on an area of normal tissue within the surgical field prior to sending all surgical specimens to pathology for examination. The fluorescence status of each specimen will then be directly correlated to the histopathological outcomes of each specimen. This study design enables the calculation of pgsitacianine sensitivity, specificity, NPV, and PPV. Additionally, Completeness of Cytoreduction (CC) scores can be calculated following SOC resection and then adjusted following the additional resection of fluorescent metastases. The schedule of events for this study is presented in [Appendix 1](#).

3.2 Study Treatment

Each patient will be administered a [REDACTED] mg/kg dose of pegsitacianine [REDACTED] [REDACTED] [REDACTED] The volume of drug and total dose will vary by patient and will depend on the patient's body weight.

4. SAMPLE SIZE AND POWER CALCULATION

The sample size for this study will be approximately 60 total subjects. This sample size is based on historical experience with similar pilot studies with the goal of informing power calculations for future studies. This study is not formally powered for hypothesis testing. A sample size of at least 40 total subjects (the originally planned sample size) will be sufficient for developing further understanding of the endpoints described herein. Sample size calculations account for non-evaluable and drop-out patients

5. ANALYSIS ENDPOINTS

5.1 Efficacy Endpoints

5.1.1 Clinically Significant Event Endpoints

The primary endpoint will include the identification of a clinically significant event (CSE) detected by pegasitacanine. CSEs will include increase in the Completeness of Cytoreduction

score following standard of care surgery, pegasitacianine detection of occult disease not otherwise known by the surgeon to exist, the detection of a positive surgical margin, and accurate identification of tumor negative SOC biopsies. A list of CSEs and their definitions is provided below.

- Detection of Occult Disease or Positive Surgical Margins – identification of tumor-containing tissue due to pegasitacianine fluorescence, confirmed via histopathological analysis, that otherwise went undetected during pre-operative imaging (PET, MRI) or by the surgeon during SOC surgery.
 - This occurs when a sample that (1) exhibits fluorescence *in situ* and (2) is pathologically-confirmed as a tumor, is obtained by fluorescence during SOC surgery.
- Tumor Negative SOC Biopsies – during SOC surgery, the surgeon will collect tissue specimens that are suspicious for disease. If those samples do not demonstrate pegasitacianine fluorescence (e.g. do not exhibit fluorescence *ex situ*) and are found to be devoid of tumor pathologically, those specimens would be included as a tumor negative SOC biopsy.
 - This occurs when a sample that (1) exhibits no fluorescence *ex situ* and (2) is pathologically-confirmed as normal tissue, is classified as suspicious tissue during SOC surgery.
- Alteration to the Completeness of Cytoreduction (CC) Score – following the completion of the SOC surgery, the surgeon will document a CC score prior to fluorescence imaging using pegasitacianine. If the surgeon finds residual disease that results in the increase of the CC score, this will be considered a CSE.

A subject with any CSE will be considered a CSE responder.

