1.2 Pegsitacianine Clinical Trial Background

Three clinical studies have been performed using pegsitacianine. The study *ON-1001: Image-Guided Surgery for Tumor Detection in Solid Tumors Using the pH Activated Micellar Probe ONM-100: The SHINE Study*, was conducted in the Netherlands at the University Medical Center Groningen and completed in 2019.¹⁹ The completed Phase 2 study, *ON-1002: A Study to Evaluate ONM-100, an Intraoperative Fluorescent Imaging Agent for the Detection of Cancer* ([NCT03735680](https://clinicaltrials.gov/ct2/show/NCT03735680)) was a multicenter trial in the United States. *ON-1004* was a Phase 1 normal healthy volunteer study to further evaluate the pharmacokinetic profile of pegsitacianine.

The purpose of the ON-1001 study was to investigate the safety, pharmacokinetics and feasibility of pegsitacianine as an intraoperative optical tracer for the detection of tumors and metastatic lymph nodes in solid cancers. Additionally, the study investigated the optimal dose range of pegsitacianine for an adequate tumor-to-background/contrast-to-noise ratio of fluorescence obtained intraoperatively and with *ex vivo* specimens using indocyanine green (ICG) compatible cameras and imaging devices. A single pegsitacianine micelle dose was administered intravenously (IV) as a one to five-minute infusion to patients in five dose cohorts (0.1, 0.3, 0.5, 0.8, and 1.2 mg/kg) with three patients per cohort in Phase 1A, and 15 patients at a dose of 1.2 mg/kg in Phase 1B. Near-infrared (NIR) imaging was conducted intraoperatively, on the back table, and postoperatively of the primary tumor, lymph nodes, and pegsitacianine guided biopsies. Additionally, the bread loaf slices from the primary tumor were also imaged postoperatively. The median tumor-to-background (TBR) value from all bread loaf slice image analysis (n = 97 slices from 27 patients) was determined to be 4.5 with an interquartile range of 3.1. Additionally, pegsitacianine demonstrated a sensitivity of 100% across all tumor types tested with a specificity of 75% and 57% in breast cancer and head and neck squamous cell carcinoma (HNSCC), respectively.¹⁹

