9.3 Rate of Clinically Significant Events

Determining the rate of clinically significant events (CSE) detected by pegasitacianine at the subject-level is the primary objective of this study. CSEs will include pegasitacianine detection of

occult disease not otherwise known by the surgeon to exist, the detection of a positive surgical margin, and accurate identification of tumor negative SOC biopsies. A list of CSEs and their definitions is provided below.

- Detection of Occult Disease or Positive Surgical Margins – identification of tumor-containing tissue due to pgsitacianine fluorescence, confirmed via histopathological analysis, that otherwise went undetected during pre-operative imaging (PET, MRI) or by the surgeon during SOC surgery
 - This occurs when a sample that (1) exhibits fluorescence *in situ* and (2) is pathologically-confirmed as a tumor, is obtained by fluorescence during SOC surgery.
- Tumor Negative SOC Biopsies – during SOC surgery, the surgeon will collect tissue specimens that are suspicious for disease. If those samples do not demonstrate pgsitacianine fluorescence and are found to be devoid of tumor pathologically, those specimens would be included as a tumor negative SOC biopsy
 - This occurs when a sample that (1) exhibits no fluorescence *ex situ* and (2) is pathologically-confirmed as normal tissue, is classified as suspicious tissue during SOC surgery.
- Alteration to the Completeness of Cytoreduction (CC) Score – following the completion of the SOC surgery, the surgeon will document a CC score prior to fluorescence imaging using pgsitacianine. If the surgeon finds residual disease using fluorescence imaging that results in the increase of the CC score, this will be considered a CSE

The number and proportion (with corresponding two-sided exact 95% confidence intervals) of subjects with any CSE will be reported.

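### A change in the CC score alone can make a primary-endpoint responder with no tumor confirmed by pathology, at odds with the protocol summary's definition of the primary proportion.

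*SAP*

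**What the plan says.** SAP 5.1.1 lists three kinds of CSE and then states: "A subject with any CSE will be considered a CSE responder". SAP 7.10.1.1 reports the proportion of responders, and the proportion for each CSE type, with Clopper-Pearson 95% intervals.

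- **Occult disease or positive margin:** needs fluorescence in situ and tumor confirmed by pathology.
- **Tumor-negative SOC biopsy:** needs absence of fluorescence ex situ and normal tissue confirmed by pathology.
- **CC-score change:** the SAP criterion is "If the surgeon finds residual disease that results in the increase of the CC score, this will be considered a CSE". Protocol 9.3 has "If the surgeon finds residual disease using fluorescence imaging that results in the increase of the CC score, this will be considered a CSE". Neither mentions pathology.

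The Protocol Summary (Statistical Analysis) describes the primary proportion as patients in whom fluorescence imaging found an additional metastatic deposit that was confirmed to be tumor. Its Endpoints entry ties the CSE to a single additional tumor-containing specimen and lists CC alteration as a primary endpoint in its own right. SAP section 1 gives the SAP precedence over the protocol for analysis, and SAP section 8 plans no deviations from the protocol.

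**The concern.** Two of the three routes into the numerator are checked against histology and the third is not. Under an any-event rule, the least demanding route decides who counts. A surgeon may judge fluorescent tissue to be residual disease and revise the score. If pathology then finds no tumor in any guided specimen, the criterion as written contains nothing that removes the event.

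The rate is presented as detection of metastatic disease left behind after standard surgery, and Protocol 9.1 and SAP section 4 say the study exists to inform power calculations for later trials. Unconfirmed events can only raise the rate, so any excess would carry into those calculations. False-positive fluorescence is not hypothetical for this agent: Protocol 1.2 reports an earlier study "with a specificity of 75% and 57% in breast cancer and head and neck squamous cell carcinoma (HNSCC), respectively". Those are other tumor types, so the figures show that the problem can occur, not how often it would occur here.

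**Working it through.** The plan gives no expected CSE rate, power or effect size, so there is no figure of its own to reproduce. The check has two parts: a comparison of the texts, then the arithmetic of one extra responder.

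**1. Is pathology required by another route?** The SAP lead-in describes the endpoint as "identification of a clinically significant event (CSE) detected by pegasitacanine". On timing, the SAP says "the surgeon will document a CC score prior to fluorescence imaging using pegasitacianine". SAP 3.1 says scores are adjusted after fluorescent metastases have been resected. These supply a general link to fluorescence but make no pathology result a condition. The term residual disease presumes tumor, yet neither document states what test establishes it.

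**2. When is the revised score fixed?** Protocol 6.3 has the surgeon dictate the first score during surgery, before the cavity is imaged. Neither document says when, or on what evidence, the second score is recorded. On pathology, Protocol Appendix 1 says: "Pathologic analysis of surgical specimens will take place from the conclusion of surgery and up to 10 days after". The revised score could therefore precede or follow the pathology result.

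**3. Who is affected?** Only patients with a CC change, no tumor-positive guided specimen and no tumor-negative SOC biopsy event. Anyone with another CSE is a responder regardless.

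**4. Effect per patient.** One extra responder adds 1/N:
- N=60 (planned total): 1/60 = 1.7 points.
- N=40 (original total): 1/40 = 2.5 points.

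SAP 7.10.1.1 summarizes by Group, and the Efficacy population may be smaller than the number enrolled. The step is larger in any smaller denominator.

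**5. Illustration at N=60.** The confirmed counts (15 and 30) and the added counts are assumptions. Intervals are Clopper-Pearson 95%.

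| Added unconfirmed CC-only responders | 15 confirmed | 30 confirmed |
|---|---|---|
| 0 | 25.0% (14.7–37.9) | 50.0% (36.8–63.2) |
| 1 | 26.7% (16.1–39.7) | 51.7% (38.4–64.8) |
| 3 | 30.0% (18.8–43.2) | 55.0% (41.6–67.9) |
| 6 | 35.0% (23.1–48.4) | 60.0% (46.5–72.4) |

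**6. Chance of at least one.** Let q be the assumed probability that a patient has a CC change resting on benign tissue. The expected number is 60q, and the chance of at least one is 1 − (1 − q)^60.
- q = 0.02: 1.2 expected; 1 − 0.98^60 = 70%.
- q = 0.05: 3 expected; 1 − 0.95^60 = 95%.
- q = 0.10: 6 expected; 1 − 0.90^60 = 99.8%.

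The documents give no value for q. Some of these patients would already be responders through another CSE, so the expected numbers are upper limits on the added responders.

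**The case against.** The strongest reply is that the criterion requires the surgeon to find disease, that benign tissue is not disease, and that the gap is one of wording. This is partly right: the rule does not direct that benign excisions be counted. But it names no test of disease, while the two neighboring definitions do, so a programmer following it would count the event whatever the histology.

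A reader might infer more than the documents support on four points:

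- **That the SAP cuts the CC event loose from fluorescence.** It drops the explicit condition, but the lead-in, the timing of the first score and SAP 3.1 keep a general link.
- **That the event rests wholly on judgement in the operating room.** That is documented only for the first score.
- **That the error could never be undone.** SAP 7.10.1.1 provides a listing of CSEs by patient, and SAP 7.10.2.1 lists pathology and fluorescence by specimen, so affected patients could be identified afterwards. The prespecified rate would still include them, and no table shows how many responders depend on the CC event alone.
- **That the inflation is large.** One could assume that half of patients have one guided excision with a positive predictive value of 0.6, giving 0.5 × 0.4 = 20 points. Every input is assumed, every benign excision must change the score, and overlap with other CSEs is ignored. This figure should not be used.

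It is also fair to object that requiring a tumor-positive guided specimen makes the CC event nearly redundant, since such a patient already meets the occult-disease definition in substance. That stands and should be disclosed. It agrees with the protocol summary's primary proportion, and CC change can still be reported as an endpoint of its own.

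**Conclusion.** The concern holds as a gap in the primary endpoint definition. As written in both documents, a CC change without pathology-confirmed tumor is enough to make a responder, contrary to the confirmed-tumor proportion in the protocol summary. The SAP criterion is also looser than the protocol's on fluorescence, although the SAP states that no deviations are planned.

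The size is 1.7 points per affected patient at N=60 and 2.5 at N=40, always upward. The number of affected patients cannot be derived from the documents and may be zero; the totals in the table rest on assumed counts. The study is not powered for hypothesis testing, so the consequence is bias in an estimate and in later planning based on it, not a false-positive test.

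**What to change.** Before database lock, in SAP 5.1.1 and Protocol 9.3:

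1. Count a CC-score change toward the CSE responder rate only if at least one post-SOC specimen, excised in that patient because of in situ fluorescence, is tumor-positive on the final pathology report.
2. Restore the protocol's explicit reference to fluorescence imaging in the SAP criterion.
3. State when the revised CC score is recorded and on what evidence.
4. Keep reporting all CC changes, confirmed and unconfirmed, as a separate component, and show the responder rate with and without patients who qualify through the CC event alone.
5. Bring the Protocol Summary, Protocol 9.3 and SAP 5.1.1 into line on whether confirmed tumor is required.

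The cost is wording and one extra table row, using pathology already collected. The responder rate may be slightly less favorable, and the CC event will add few or no responders beyond the occult-disease CSE. The SAP should say so openly.
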